### 5.3.5 Derivation of the General Anxiety Disorder-7 Total Score

General Anxiety Disorder-7 (GAD-7) scores seven individual item scales by assigning scores of 0, 1, 2, and 3, to the response categories of “not at all”, “several days”, “more than half the days”, and “nearly every day”, respectively. The GAD-7 total score is calculated using the method described in the instruction manual [3], by summing the individual item scales to give a total score between 0 and 21. If any of the individual item scores are missing the total score will not be calculated.

Total aggregated score will be used to categorise severity of generalised anxiety disorder as per table 2.

**Table 2: Anxiety severity categories for GAD-7 total score**

GAD-7 Total Score Range	Anxiety Severity
0 – 4	None/Minimal
5 – 9	Mild
10 – 14	Moderate
15 – 21	Severe

### 5.3.6 Derivation of the Patient Health Questionnaire-9 Total Score

Patient Health Questionnaire-9 (PHQ-9) scores nine individual item scales by assigning scores of 0, 1, 2, and 3, to the response categories of “not at all”, “several days”, “more than half the days”, and “nearly every day”, respectively. PHQ-9 total scores are calculated using the method described in the instruction manual [3], by summing the individual item scales to give a total score between 0 and 27. If any of the individual item scores are missing the total score will not be calculated.

Total aggregated score will be used to categorise severity of depression as per table 3.

Table 3: Depression severity categories for PHQ-9 total score

PHQ-9 Total Score Range	Depression Severity
0 – 4	None/Minimal
5 – 9	Mild
10 – 14	Moderate
15 – 19	Moderately Severe
20 – 27	Severe

### 5.3.7 Derivation Functional Assessment of Chronic Illness Therapy Fatigue Scale Total Score

Total scores from version 4 of the Functional Assessment of Chronic Illness Therapy (FACIT) fatigue scale can be calculated using the following algorithm, as per the scoring guidelines [4]:

- If less than 50% of the items have been completed total score should not be calculated.
- Otherwise, the item scores should be reversed, as 4 – Item score, for all items except the questions “I have energy” and “I am able to do my usual activities”.
- Sum the converted values.
- Multiply the summed values by the total number of items on the scale (13) and divide by the number of answered items.

This algorithm will give total score on a scale between 0 and 52, where a higher total score indicates lower level of fatigue.

### 5.3.8 Derivation of the Brief Pain Inventory Composite Scores

Overall pain severity score will be calculated as the mean of questions 3 to 6 of the brief pain inventory short form. If any of questions 3 to 6 are unanswered the overall pain severity score should not be calculated.

The pain interference score is calculated as the mean of the scales under question 9 of the brief pain inventory. The pain interference score can be calculated provided at least 4 of the 7 interference scales have been completed, otherwise the pain interference score should be missing.

Both of the above measures are as defined in the brief pain inventory user guide [5].

### 5.3.9 Derivation of Oxygen Variables

The fraction of inhaled oxygen ( $\text{FiO}_2$ ) can be calculated from the given oxygen flow in L/min using Table 4 below for all devices except the Venturi masks [12].

**Table 4: Calculation of  $\text{FiO}_2$  for all Devices except Venturi Masks**

Flow (L/min)	$\text{FiO}_2$
1	0.28
2	0.38
3	0.43
4	0.50
5	0.56
6	0.62
7	0.64
8	0.66
9	0.71
10	0.73
11	0.75
12	0.76
13	0.77
14	0.79
15	0.81

Oxygen flow should be taken from the Vital Signs page of the CRF. Any oxygen flow records which are expressed as decimals should be rounded up to the nearest integer. For any oxygen flow records expressed as a range the maximum value should be taken to calculate  $\text{FiO}_2$ .

For Venturi masks the oxygen flow should be presented in the raw data as  $\text{FiO}_2$ . However if the oxygen flow is presented in L/min the standard Venturi mask conversion should be used as per Table 5.

## Statistical Analysis Plan (RotW)

Final v1.0, 08FEB2022

SG018

**Table 5: Calculation of FiO2 for Venturi Masks**

Flow (L/min)	FiO 2
2	0.24
4	0.28
6	0.31
8	0.35
10	0.40
15	0.60

Any oxygen flow volume which does not appear in the above table should be rounded up to the closest volume available.

For summary statistics FiO2 should be expressed as a percentage.

The Saturated Oxygen (SpO2) / FiO2 ratio is calculated as the SpO2 (expressed as a decimal) / FiO2 at the corresponding visit.

## 6 Sample Size

A sample size of 610 subjects in total using a 1:1 randomisation ratio (305 subjects per treatment arm) has been chosen to provide at least 90% power to detect a hazard ratio of 1.45 in time to hospital discharge and a hazard ratio of 1.7 in time to recovery and at least 95% power to declare statistical significance on at least one of the primary endpoints. This sample size has been calculated using a global 2-sided alpha level of 0.05 and adjusting for the Hochberg procedure to allow for multiple comparisons. This sample size also allows for an interim analysis to assess futility after the first 300 randomised subjects (150 subjects per treatment arm) have completed the Day 35 assessment or have withdrawn from the study. The futility analysis is planned to be non-binding.

The power of the study was confirmed via simulation as follows:

Time to recovery and time to discharge in the placebo subjects were drawn from exponential distributions with rate parameters:

$$\text{Placebo Time to Sustained Recovery} \sim \text{Exp}\left(\frac{\log\left(\frac{100}{70}\right)}{28}\right) \text{ and}$$

$$\text{Placebo Time to Sustained Discharge} \sim \text{Exp}\left(\frac{\log\left(\frac{100}{30}\right)}{28}\right)$$

In the simulations, this gives the placebo arm:

- a median time to recovery (50% recovery) of approximately 54.4 days and a 30% recovery at exactly 28 days

## Statistical Analysis Plan (RotW)

Final v1.0, 08FEB2022

SG018

- a median time to discharge (50% discharge) of approximately 16.1 days and a 70% discharge at exactly 28 days

Assumed hazard ratios (SNG vs Placebo) for recovery and discharge of 1.35 and 1.7 respectively, this data can be simulated:

$$\text{Active Time to Sustained Recovery} \sim \text{Exp}\left(\frac{\log\left(\frac{100}{70}\right)}{28 * 1.35}\right) \text{ and}$$

$$\text{Active Time to Sustained Discharge} \sim \text{Exp}\left(\frac{\log\left(\frac{100}{30}\right)}{28 * 1.7}\right)$$

This gives the active arm:

- a median time to recovery (50% recovery) of approximately 40.3 days and a 30% recovery at approximately 21.5 days
- a median time to discharge (50% discharge) of approximately 9.5 days and a 70% discharge at approximately 16.5 days

It was additionally assumed that study withdrawal followed an exponential distribution on both treatment arms

$$\text{Withdrawal From Study} \sim \min\left(\text{Exp}\left(\frac{\log\left(\frac{100}{75}\right)}{28}\right), 28\right)$$

so that in the simulations, on average 25% of patients withdraw early from the study (i.e. before Day 35), and the other 75% have complete follow-up.

All patients were assumed to contribute to the primary endpoints up to their withdrawal from the study, thus patients who withdrew may still meet one or both primary endpoints. Patients who withdrew early without meeting the primary endpoint(s) were censored in the simulation analyses. All patients were administratively censored at the last time point (on Day 28).

An interim analysis at which both primary endpoints were assessed was simulated using the data from the first 300 randomised subjects (150 on each treatment arm). The simulated study was stopped for futility if the Z statistic (calculated as the partial likelihood log hazard ratio for SNG vs Placebo divided by its standard error) for both primary analyses was less than 1.4. Otherwise the simulated study continued to recruit the remaining 310 subjects (155 on each treatment arm) and the pooled (pre-interim and post-interim) simulated data was analysed at the final analysis.

The power of the overall study to meet both primary endpoints was simulated as over 90%. The power to meet at least one primary endpoint was approximately 95%.

In the case of the complete absence of efficacy in one of the primary endpoints the power to meet the other primary endpoint was approximately 85%.

Additional simulations were performed in which a statistical dependency was created between the two primary endpoints while maintaining the same marginal distributions. The power to show statistical significance in at either endpoint was maintained but the power to reach statistical significance in both primary endpoints was (as expected) slightly increased.

For further information refer to the simulation report in [Appendix II](#).

## 7 General Considerations

### 7.1 Analysis Populations

#### 7.1.1 Intent-to-Treat Population

The Intent-to-Treat (ITT) analysis population will include all randomised patients. The ITT population will be the primary analysis population for efficacy analyses and will summarise patients by their randomised treatment group.

#### 7.1.2 Per Protocol Population

The Per Protocol (PP) analysis population will include all patients within the ITT population who do not have any protocol deviations with an impact on efficacy on or prior to Day 35 and will be used for supportive analyses of efficacy endpoints, as appropriate. Relevant protocol deviations may include, but are not limited to the following:

- Patient was not admitted to hospital due to the severity of their COVID-19.
- Patient did not have a positive RT-PCR virus test by RT-PCR at screening. Evidence of ongoing SARS-CoV-2 infection for more than 3 weeks, confirmed by a validated molecular assay or validated antigen assay.
- OSCi score at baseline was  $\neq 4$ .
- Patient is receiving mechanical ventilation or is in intensive care prior to randomisation.
- Patient could not use a nebuliser with a mouthpiece at baseline.
- Patient failed to receive at least two full doses of the scheduled doses in the first 3 days after randomisation.
- No post baseline OSCi assessments were performed.
- Patient was not discharged from hospital for reasons other than the severity of their condition.

Blinded protocol deviation data will be reviewed routinely in accordance with the protocol deviation plan. Decisions regarding the exclusion of patients from the PP population who have completed the day 35 assessments or who have withdrawn from the study and have all data available and no outstanding data queries will be made during these meetings. Following completion of the study database the status of all patients with regards to the PP population will be reviewed and confirmed.

Following study unblinding, the randomisation schedule will be used to confirm if the randomised drug was correctly administered at each assessment by comparing the syringe numbers entered into the database against the syringe numbers in the material lists. Patients randomised to SNG001 will be excluded from the PP population if SNG001 was administered on less than 2 occasions in the first 3 days of treatment (either missed doses or incorrectly treated with placebo). For patients randomised to Placebo,

assessments of OSCi, BCSS, NEWS2 and EQ-5D-5L conducted on or after the first dose of SNG001 will be excluded from analyses of the PP population.

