- b. Progression to intubation or death, defined by the WHO OSCi score of 6 or above within 35 days of first dose (or randomisation date if the patient is not dosed).
- c. Death within 35 days of first dose (or randomisation date if the patient is not dosed).

Secondary Endpoints:

- a. Recovery, where recovery is defined as the WHO OSCi score of 1 or below, with no rebound at subsequent assessments, at Days 7, 14, 21 and 28.
- b. Hospital discharge by Days 7, 14, 21 and 28.
- c. Improvement across the entire WHO OSCi by Days 7, 14, 21 and 28.
- d. Changes in breathlessness, cough and sputum scale (BCSS) score during the study

period, including disaggregated breathlessness and cough scores.

- e. Changes in National Early Warning Score 2 (NEWS2) during the hospitalisation period.
- f. Daily assessment of COVID-19 symptoms and limitation of usual activities.
- g. Quality of life measured using EQ-5D-5L.
- h. Long-COVID-19 symptoms.
- i. Safety and tolerability – vital signs, AEs, concomitant medications, and immunogenicity.

Exploratory Endpoint:

CCI	CCI
	CCJ
CCI	

Inclusion criteria:

To be eligible for randomisation into this study, each patient must fulfil the following criteria:

1. Male or female, ≥ 18 years of age at the time of consent.
2. Admitted to hospital due to the severity of their COVID-19.¹
3. Positive virus test for SARS-CoV-2 using a validated molecular assay or antigen assay. Patients who had a positive virus test for SARS-CoV-2 prior to hospitalisation will be randomised no later than 48 hours after hospital admission. If the virus test is performed more than 96 hours prior to hospitalisation, the test will have to be repeated in the hospital prior to randomisation. Only patients whose repeated virus test is positive will be randomised, no later than 48 hours after confirmation of SARS-CoV-2 infection.
- Patients who had their first positive virus test for SARS-CoV-2 after hospitalisation will be randomised no later than 48 hours after confirmation of SARS-CoV-2 infection.
4. Require oxygen therapy via nasal prongs or mask (WHO OSCI score of 4).
5. Provided informed consent.
6. Female patients must be ≥ 1 year post-menopausal, surgically sterile, or using a highly effective method of contraception. Acceptable highly effective methods of contraception include;
 - bilateral tubal occlusion
 - intrauterine device (provided coils are copper-banded)
 - levonorgestrel intrauterine system (e.g., MirenaTM)

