3.1 Criteria for Inclusion and Exclusion

3.1.1 Inclusion Criteria

To be eligible for randomisation into this study, each patient must fulfil the following criteria:

1. Male or female, ≥ 18 years of age at the time of consent.
2. Admitted to hospital due to the severity of their COVID-19¹.
3. Positive virus test for SARS-CoV-2 using a validated molecular assay or validated antigen assay.

Patients who have a positive virus test for SARS-CoV-2 prior to hospitalisation will be randomised no later than 48 hours after hospital admission. If the virus test is performed more than 96 hours prior to hospitalisation, the test will have to be repeated in the hospital prior to randomisation. Only patients whose repeated virus test is positive will be randomised, no later than 48 hours after confirmation of SARS-CoV-2 infection.

¹ Patients admitted to the hospital for reasons that are non-COVID-19 related, who subsequently develop clinical symptoms of COVID-19, test positive for SARS-CoV-2, and require prolongation of their hospital admission, as a consequence of COVID-19, and require treatment with supplemental oxygen (via nasal prongs or mask), must be discussed with the Sponsor's medical monitor prior to randomisation, to assess suitability for the trial.

Patients who have their first positive virus test for SARS-CoV-2 after hospitalisation will be randomised, no later than 48 hours after confirmation of SARS-CoV-2 infection.

4. Require oxygen therapy via nasal prongs or mask (WHO OSCI score of 4).
5. Provided informed consent.
6. Female patients must be ≥ 1 year post-menopausal, surgically sterile, or using a highly effective method of contraception. Acceptable highly effective methods of contraception include:
 - bilateral tubal occlusion
 - intrauterine device (provided coils are copper-banded)
 - levonorgestrel intrauterine system (e.g., CCI [REDACTED])
 - medroxyprogesterone injections (e.g., CCI [REDACTED])
 - etonogestrel implants (e.g., CCI [REDACTED], CCI [REDACTED])
 - normal and low dose combined oral pills
 - norelgestromin/ ethinylestradiol transdermal system
 - intravaginal device (e.g., ethinylestradiol and etonogestrel), desogestrel (e.g., CCI [REDACTED])
 - total sexual abstinence (defined as refraining from heterosexual intercourse)
 - vasectomised sexual partner.

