**5 Study Methods****5.1 General Study Design and Plan**

610 adults,  $\geq 18$  years of age with Severe Acute Respiratory Syndrome Coronavirus 2 (SARS-CoV-2) infection confirmed by a positive virus test using a validated molecular assay e.g. Reverse Transcription Polymerase Chain Reaction (RT-PCR) or antigen assay, e.g. Sofia 2 SARS Antigen FIA, who are hospitalised due to COVID-19 and require oxygen therapy, either via nasal prongs or a mask, but do not require high-flow nasal oxygen therapy, non-invasive ventilation (Continuous Positive Airway Pressure [CPAP] or /bilevel positive airway pressure [BiPAP]) treatment or endotracheal intubation will be randomised 1:1 to receive SNG001 two syringes (305 patients) or placebo two syringes (305 patients).

Patients will receive a dose of SNG001 or placebo once a day for 14 days and will be followed for up to 90 days after the first dose of study medication. Study data will be collected from patients daily until day 35, as per the study schedule.

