#### 9.1.1.4 *Supportive Estimands*

A supportive estimand of the primary endpoint will estimate the hazard ratio of SNG001 versus placebo for the time to hospital discharge of patients in the per protocol population. Reasons for excluding patients from the PP population are described in [Section 7.1.2](#). Of note, many of the reasons are based on assessments prior to randomisation and treatment and so the exclusions are independent of treatment. Intercurrent events will be handled as per table 9.

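### The per-protocol list in SAP 7.1.2 names RT-PCR at screening only, so if applied literally it could remove patients who met inclusion criterion 3 by another accepted test

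*SAP*

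**What the plan says.** **The PP bullet.** SAP 7.1.2 defines the PP population as ITT patients without a protocol deviation bearing on efficacy up to Day 35, as Protocol 8.3 does. It then gives examples, introduced by "Relevant protocol deviations may include, but are not limited to the following". One of them is "Patient did not have a positive RT-PCR virus test by RT-PCR at screening". The same bullet continues with a second, separate criterion: infection ongoing for more than three weeks, which may be shown by a molecular or an antigen assay.

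**The eligibility rule.** Protocol 3.1.1, item 3, requires "Positive virus test for SARS-CoV-2 using a validated molecular assay or validated antigen assay". The synopsis says the same in nearly the same words: "Positive virus test for SARS-CoV-2 using a validated molecular assay or antigen assay". Protocol Section 3 mentions RT-PCR only as an example of a molecular assay. SAP 5.1 follows the protocol: its description of the population admits patients on a molecular assay "or antigen assay, e.g. Sofia 2 SARS Antigen FIA, who are hospitalised due to COVID-19 and require oxygen therapy".

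**Timing.** Item 3 also sets a rule for early tests, with randomisation as the deadline: "If the virus test is performed more than 96 hours prior to hospitalisation, the test will have to be repeated in the hospital prior to" that point. A positive test taken closer to admission than that needs no repeat.

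**Who decides.** SAP 7.1.2 adds that "Blinded protocol deviation data will be reviewed routinely in accordance with the protocol deviation plan". The PP status of every patient is confirmed once the database is complete.

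**The concern.** A PP set is meant to hold the patients who followed the protocol. A patient enrolled on a validated antigen test inside the permitted window did follow it on this point, yet fits a listed reason for exclusion. The same holds for a patient enrolled on a validated molecular assay other than RT-PCR. It arguably holds for one whose accepted positive test was taken before screening, since the SAP bullet is tied to screening and criterion 3 is not.

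The PP set carries the supportive estimands for both primary endpoints (SAP 9.1.1.4 and 9.1.2.4) and all three key secondary endpoints (9.2.1.4, 9.2.2.4 and 9.2.3.4). It is also used to repeat several secondary analyses (SAP Table 7). At stake is whether those analyses describe protocol-compliant patients, and with what precision.

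**Working it through.** **1. The texts side by side**

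| Question | Protocol 3.1.1 item 3 and SAP 5.1 | SAP 7.1.2 bullet |
|---|---|---|
| Antigen assay accepted? | Yes | Not mentioned |
| Molecular assay other than RT-PCR accepted? | Yes; RT-PCR is an example only | Not mentioned |
| Accepted positive test taken before hospitalisation? | Yes (item 3), without repeat if no more than 96 hours before | Refers to a test at screening |

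**2. Against the PP definition.** Exclusion requires a protocol deviation. A patient positive on an accepted assay within the window meets item 3, so there is no deviation on this point. Applied literally, the bullet therefore contradicts the sentence that it illustrates.

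**3. Is it a declared change?** SAP Section 15 lists the departures from the protocol: the seven-day rebound period, the covariate set, and the handling of medications in the PP estimands. A restriction to RT-PCR is not among them.

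**4. Possible size.** The plan gives no figure to reproduce. The share of patients enrolled on an antigen test alone, *f*, is not in the documents, so the values below are assumptions. Total N = 610 comes from Protocol 8.1.

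- Patients lost = 610 × *f*
- Standard-error ratio = 1/√(1 − *f*), taking information as proportional to the number of patients and starting from all 610, before any other PP exclusion

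| *f* (assumed) | Patients lost | Standard-error ratio |
|---|---|---|
| 10% | 61 | 1/√0.9 = 1.05 |
| 20% | 122 | 1/√0.8 = 1.12 |
| 30% | 183 | 1/√0.7 = 1.20 |

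**5. Background on power.** The inputs are from Protocol 8.1: placebo event rates at Day 28 of 70% (discharge) and 30% (recovery), 25% dropout, and hazard ratios of 1.45 and 1.7. With exponential event rate λ and dropout rate w, expected events per arm are n × λ/(λ + w) × (1 − exp(−28(λ + w))). Over both arms this gives about 418 discharges and 202 recoveries. The Schoenfeld approximation, Φ(ln HR × √(events/4) − 1.96), gives about 97% power for each endpoint at two-sided 0.05. At two-sided 0.025 it is about 94%, consistent with the plan's stated minimum of 90%.

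Power at two-sided 0.05 in a smaller PP set:

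| *f* (assumed) | Discharge | Recovery |
|---|---|---|
| 10% | 95.0% | 94.8% |
| 20% | 92.5% | 92.2% |
| 30% | 88.9% | 88.5% |
| 40% | 83.7% | 83.3% |

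The plan sets no power target for the PP set, so this shows scale only.

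**The case against.** The strongest reply is that nobody need be excluded. The list is permissive and non-exhaustive, the governing definition demands a real deviation, and the decisions are taken in blinded review under a deviation plan that is not among these documents. The wording also looks like a drafting slip: RT-PCR appears twice in one phrase, and the next sentence of the bullet recognises antigen assays. On that view the definition keeps the antigen-positive patient and the bullet is only loosely worded.

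Much of this stands. A reader might infer that the plan commits the sponsor to removing these patients. The documents do not support that; they make removal possible, not certain. The reply does not clear the bullet, however. SAP 9.1.1.4 says "Reasons for excluding patients from the PP population are described in" Section 7.1.2, and the later supportive-estimand sections repeat the reference. Those applying the list would hold two instructions that disagree, and the SAP does not say which prevails.

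It is also fair to say that the PP analyses are only supportive. ITT is the primary efficacy population, and the Hochberg and sequential tests apply to ITT estimands. The calculation above adds that even an assumed 40% loss would leave about 83% to 84% power under the planning inputs. This limits the seriousness of the point but leaves the contradiction in place.

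**Conclusion.** The inconsistency is real and the SAP bullet is wrong as written: it conflicts with inclusion criterion 3, with SAP 5.1 and with the PP definition it sits under. The consequence is conditional. If the bullet is applied literally, protocol-compliant patients could be dropped, at a cost in precision and representativeness in the supportive PP analyses only. The patient counts and standard-error ratios rest on assumed antigen-only shares; the true share is unknown and could be near zero.

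Three further inferences are tempting and not supported:

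- **Bias between arms.** The eligibility test precedes randomisation, so exclusion on it should not depend on treatment.
- **Damage to the main conclusions.** The ITT primary and key secondary analyses do not use this list.
- **A shift in the country or site mix of the PP set.** This would require test type to vary by place, and neither document describes testing practice by country or site.

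**What to change.** In SAP 7.1.2, replace only the first sentence of the bullet with: *Patient did not have a positive validated molecular or antigen SARS-CoV-2 test within the window of inclusion criterion 3.*

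Keep the second sentence, on infection ongoing for more than three weeks, as a bullet of its own. It reflects exclusion criterion 1 in Protocol 3.1.2 and would be lost if the whole bullet were overwritten.

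If the sponsor does want a PP set confined to RT-PCR-confirmed patients, that should be stated and justified in SAP Section 15 as a change from the protocol.

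The cost is one reworded sentence and one bullet split in two, with no effect on the ITT analyses. The change should be made before unblinding, and the protocol deviation plan should be checked for the same wording.
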